4.8 Intralesional IL-2

In an attempt to take advantage of the robust immune activating effects of IL-2 but avoid the toxicity of high dose systemic IL-2 we and others have investigated the use of intralesional IL-2 injections.

4.8.1 Intralesional IL-2 in Advanced NSCLC

[figure not shown]
A number of studies have evaluated local IL-2 administration for primary or metastatic malignant lung lesions. Lissoni et al examined intracavitary IL-2 treatment for malignant pleural effusions and demonstrated a 72% response rate and the only toxicity was fevers in 6% of patients [41]. A study from Italy has tested systemic HD-IL-2 in combination with intralesional IL-2 for NSCLC [42]. This trial reported a 25% response rate and a 62.5% disease control rate.

No unexpected toxicities were observed from the intralesional injection of IL-2 although one third of patients experienced pneumothorax from the repeated transparietal injections. Overall intralesional toxicity rates from this trial are difficult to determine given the use of systemic high dose IL-2. Due to the risk of pneumothorax from our transparietal lesions, our trial does not allow for the treatment of lung lesions.

4.8.3 Intralesional IL-2 in Metastatic Renal Cell Carcinoma

Intralesional IL-2 has been tested in patients with progressive metastatic renal cell carcinoma (RCC) in a phase I trial in combination with granulocyte macrophage colony-stimulating factor (GM-CSF) and IFN-alpha[49]. The results were promising: three of eight patients with progressive metastatic RCC after nephrectomy achieved complete remission. Huland et al. introduced IL-2 inhalation therapy for 116 patients with pulmonary and mediastinal metastases from RCC who could not tolerate HD-IL-2 [50]. Progressive pulmonary metastases responded dramatically in 15% of the patients for a median of 15.5 months and were stabilized in 55% of patients for a median of 6.6 months. Toxicity associated with IL-2 inhalation was local and consisted mainly of cough and patients were able to be treated on an outpatient basis.

4.8.4 Intralesional IL-2 in Metastatic Head and Neck Squamous Cell Carcinoma

Timai et al. [47] reported a 42 % response in the treatment of oral squamous cell carcinoma and reported the complete absence of adverse effects with this regimen although it should be noted that the dose of intralesional IL-2 they incorporated was significantly lower than that reported for melanoma lesions. A phase III trial showed that patients with resectable SCCs of the oral cavity and oropharynx treated with perilymphatic intralesional administration of low-dose IL-2 had longer disease free and overall survival [51].

Taken together these data demonstrate clear efficacy and safety for the use of intralesional IL-2 for the treatment of malignant lesions at dermal, subcutaneous, and non-pulmonary visceral sites. A summary of relevant toxicities from intralesional IL-2 can be found in Table 1. It is important to note that most of these trials employed concomitant therapies including concomitant

immunotherapy. Critically, of 187 patients treated across these trials only two (1.1%) experienced grade 3 toxicity.

Table 1. Common Adverse Events with Intralesional IL-2 in $\geq 10\%$ of Patients

	N	Site	Grade 1/2 Injection Site	Grade 1/2 Injection Pain	Grade 1/2 Fever / Chills / Flu-like Symptom s	Grade 1/2 Fatigue	Grade 1/2 Nausea	Grade 1/2 Local Infection	Grade 1/2 Stomach Pain	Grade 1/2 Diarrhea	Grade 1/2 Headache
Radny 2003	24	Dermal, SQ	100%	--	58%	46%	41%	--	17%	12%	12% (4% Gr 3)
Green 2007	13	Dermal, SQ	100%	--	Several patients	--	15%	15%	--	--	--
Weide 2010	52	Dermal, SQ	98%	78%	58%	36%	34%	--	--	--	--
Boyd 2011	39	Dermal, SQ	--	100%	85%	--	--	--	--	--	--
Shi 2015	11	Dermal, SQ	100% (9% Gr3)	--	55%	--	--	--	--	--	--
Timar 2005	39	Oral mucosa	--	--	--	--	--	--	--	--	--
Ferlazzo 1997	9	Liver	--	--	Several Patients	--	--	--	--	--	--

4.8.5 IL-2 Dosing Rationale

[figure not shown]
Four doses of intralesional IL-2 will be evaluated: -1) 1×10^6 IU; 1) 3×10^6 IU; 2) 7×10^6 ; 3) 15×10^6 IU. These dose levels were selected based on the clinical data described above and our clinical experience with intralesional IL-2. One of the largest reports, which included 48 patients with metastatic melanoma, indicates that this approach is highly effective with a 70% response rate of injected lesions and limited grade 1-2 toxicity [43]. This study incorporated an initial dose of 3 million IU which was escalated within each patient as tolerated. Treatments occurred 3x weekly for a median duration of 6 weeks and the dose was escalated up to a maximum of 16 million IU. Additionally, the selected dose levels are institutional practice at UC Davis have been reported in several clinical series [44, 45] and we have recently published these guidelines for the use of intralesional IL-2 that have been adopted by NCCN [46].

We will initiate the trial at Dose level 3 and de-escalate to lower dose levels as needed to establish the MTD. We have chosen this approach for four reasons: 1) Two patients have already been treated using this same treatment protocol at dose level 3 on our pilot trial UCDCC 269 with no evidence of dose limiting toxicities. 2) This allows patients on trial to begin treatment at the dose believed to be effective and previously shown to be safe and therefore provides the greatest potential benefit for study participants. 3) Even at dose level 3 the first dose given to patients is 3×10^6 IU, thus the intrapatient dose escalation which is the standard approach for intralesional IL-2 administration provides an additional safety assessment. 4) Dose level 3 is our institutional practice which has been administered to numerous patients off trial with limited toxicities.

4.9 Intralosomal Interleukin-2 in Combination with Radiotherapy or Checkpoint Blockade Therapy.

Although HD-IL-2 has been combined with RT there is limited published data examining intralosomal IL-2 in combination with RT. Preliminary mouse model data generated in our lab demonstrates a synergistic anti-tumor effect to this combination similar to systemic HD-IL-2 combinations.

Figure 4. Radiotherapy + Intralosomal IL-2 in a murine melanoma model

Furthermore, in two patients with metastatic melanoma who received intralosomal IL-2 and palliative radiotherapy we observed complete regression of irradiated / injected lesions and long term progression free survival without any evidence of unexpected or additive toxicity. Taken together these preclinical studies and clinical observations suggest synergy between radiotherapy and intralosomal IL-2.

Figure 5. Complete regression observed in irradiated/injected metastatic melanoma lesions

A recent report at ASCO 2015 has also demonstrated the safety and efficacy of intralosomal IL-2 in combination with intralosomal CTLA-4 checkpoint blockade. Twelve patients were treated with no dose limiting toxicities and a 75% response rate at untreated lesions.

4.10 Intralesional IL-2 + RT in patients refractory to PD-1/PD-L1 checkpoint blockade

The advent of checkpoint blockade immunotherapy has revolutionized the management of metastatic cancer. Despite the promising evidence for deep and durable responses with these agents the majority of patients fail to respond. It is hypothesized that a novel strategy combining radiotherapy and intralesional interleukin-2 (IL-2), a signaling molecule and member of the cytokine family involved in the activation of leukocytes and lymphocytes, may overcome resistance to checkpoint blockade therapy and offer significant clinical benefit to patients who fail to respond to checkpoint blockade alone. We are proposing a bold combinatorial immunotherapy strategy consisting of radiotherapy (RT), intralesional IL-2, and check-point blockade for patients with metastatic NSCLC, melanoma, RCC, and HNSCC who have progressed after checkpoint inhibition. IL-2 can upregulate PD-1 expression and activate T-cells. There is data supporting combination therapies with IL-2 and checkpoint blockade, IL-2 and radiotherapy, and checkpoint blockade and radiotherapy but clinical data is limited and the triple combination has never been tested. IL-2 + checkpoint blockade was recently tested in a small clinical trial and showed promising results but RT was not included in this trial. As outlined above RT has been demonstrated to increase the efficacy of both IL-2 and checkpoint blockade. We believe that the triple combination of radiotherapy + IL-2 + checkpoint inhibition will be highly effective as RT + IL-2 can serve highly activate the immune system and checkpoint blockade can reverse the immune suppressive pathways induced by tumor and therapy.

We hypothesize that the triple combination of radiotherapy + intralesional IL-2 + Pembrolizumab will be highly effective and convert patients with primary or secondary resistance to checkpoint blockade into responders. We hypothesize that the combination of intralesional IL-2 with radiotherapy will act as an “in-situ” vaccine inducing an anti-tumor immune response and increasing tumor infiltrating lymphocytes thereby overcoming a major mechanism of checkpoint blockade resistance while the continuation of PD-1 inhibition will be critical for overcoming tumor and therapy induced immune suppression. This trial will incorporate robust correlative assays to provide insights into mechanisms of primary and secondary resistance to checkpoint blockade and how this therapy may overcome that resistance. This trial, although small, has the potential to drastically advance both our understanding and treatment of PD-1/PD-L1 checkpoint blockade resistant cancer. We reviewed the National Institutes of Health Clinical Research Studies (<https://clinicaltrials.gov/>), which are open and available for patient enrollment, and there are no open trials looking at the effects of intralesional IL-2 combined with radiation and checkpoint inhibition. Collectively, this provides the basis of our proposal which is extensively detailed below.

4.11 Biomarkers

One of the major shortcomings of immunotherapy trials has been the lack of in-depth correlative studies to help identify the mechanism of action, identify biomarkers of response, and explain the mechanisms governing treatment response or failure. To address this, we plan to perform in depth immunological analysis of patient blood and tumor samples. This study incorporates serial tissues samples pre- treatment, during therapy, and at progression. The design of this study allows us to compare immune mechanisms pre- to post-therapy.

Tumor PD-L1 expression has been linked to response rates of PD-1 checkpoint blockade[7]. Pre-clinical data suggests that radiotherapy may upregulate intratumoral PD-L1 expression[52] but little is known about the dose response of these effects. Additionally, little is known about how the pattern of expression (i.e., tumor cells vs. infiltrating immune cells) affects response. Data presented at ASCO and SITC indicate that durvalumab monotherapy response rates in NSCLC are 27% in PD-L1 positive tumors and 5% in PD-L1 negative tumors. TILs and a T-cell inflamed phenotype have been linked with response to CTLA-4 checkpoint blockade in melanoma [53, 54]. Exclusion of T-cells in the tumor microenvironment has also been linked with lack of response to checkpoint inhibition [55] with down-regulation of CCL4 mediated dendritic cell recruitment as one potential mechanism [55]. RT has been demonstrated to induce TILs[56] and may potentially overcome this mechanism of resistance to checkpoint blockade. Our unpublished data suggests that RT can induce CCL4 expression and increase TILs. Likewise, IL-2 may expand intratumoral T-cells helping to circumvent the mechanisms of checkpoint blockade resistance.

Mutational burden and antigenic load are thought to represent a surrogate for tumor antigenicity and have been linked with response to checkpoint blockade in NSCLC [57]. Whether mutational load is a true indicator of tumor antigenicity and how this correlates with response to this combinatorial approach is unknown.

5.0 METHODOLOGY

5.1 Entry Criteria

5.1.1 Diagnosis/Condition for Entry into the Trial

Advanced solid malignancy or lymphoma with progression on PD-1/PD-L1 checkpoint blockade.

5.1.2 Subject Inclusion Criteria

1. Adults ≥ 18 years of age with histologically proven, advanced solid malignancy or lymphoma.
2. Clinical and/or radiographic progression on checkpoint blockade therapy (either after prior response or primary refractory).
3. ECOG (Eastern Cooperative Oncology Group) performance status score of 0 – 1 (Appendix 1)
4. Presence of a candidate treatment lesion (subcutaneous, muscular, nodal, or other soft tissue lesions, and other lesions will also be considered with PI approval) accessible and safe for radiotherapy and serial intralesional injections.
5. Presence of at least one target lesion (distinct from treatment lesion and outside of treatment lesion radiation field) evaluable for response by irRECIST
6. Life expectancy ≥ 6 months
7. Demonstrate adequate organ function as defined in Table 2, all screening labs should be performed within 10 days of treatment initiation.

Table 2. Adequate Organ Function Laboratory Values

System	Laboratory Value
Hematological	
Absolute neutrophil count (ANC)	$\geq 1,500$ /mcL
Platelets	$\geq 100,000$ / mcL
Hemoglobin	≥ 9 g/dL or ≥ 5.6 mmol/L without transfusion or EPO dependency (within 7 days of assessment)
Renal	
Serum creatinine	≤ 1.5 X upper limit of normal (ULN)
OR	
Measured or calculated ^a creatinine clearance (GFR can also be used in place of creatinine or CrCl)	≥ 60 mL/min for subject with creatinine levels > 1.5 X institutional ULN
Hepatic	
Serum total bilirubin	≤ 1.5 X ULN OR Direct bilirubin \leq ULN for subjects with total bilirubin levels > 1.5 ULN
AST (SGOT) and ALT (SGPT)	≤ 2.5 X ULN OR ≤ 5 X ULN for subjects with liver metastases
Albumin	≥ 2.5 mg/dL

Coagulation	
International Normalized Ratio (INR) or Prothrombin Time (PT)	$\leq 1.5 \times$ ULN unless subject is receiving anticoagulant therapy as long as PT or PTT is within therapeutic range of intended use of anticoagulants
Activated Partial Thromboplastin Time (aPTT)	$\leq 1.5 \times$ ULN unless subject is receiving anticoagulant therapy as long as PT or PTT is within therapeutic range of intended use of anticoagulants

^aCreatinine clearance should be calculated per institutional standard.

8. Deleted as of Amendment 09/07/2022.
9. Female subject of childbearing potential should have a negative urine or serum pregnancy within 4 days prior to receiving the first dose of study medication. If the urine test is positive or cannot be confirmed as negative, a serum pregnancy test will be required.
10. Female subjects of childbearing potential (Section 5.7.2) must be willing to use an adequate method of contraception as outlined in Section 5.7.2 – Contraception, for the course of the study through 120 days after the last dose of study medication.
Note: Abstinence is acceptable if this is the usual lifestyle and preferred contraception for the subject.
11. Male subjects of childbearing potential (Section 5.7.2) must agree to use an adequate method of contraception as outlined in Section 5.7.2 - Contraception, starting with the first dose of study therapy through 120 days after the last dose of study therapy.
Note: Abstinence is acceptable if this is the usual lifestyle and preferred contraception for the subject.
12. Signed informed consent.
13. Ability to comply with the protocol.
14. Systolic blood pressure ≥ 80 .
15. Deleted as of Amendment 09/07/2022.
16. Deleted as of Amendment 09/07/2022.

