7.2.3 Laboratory Procedures/Assessments

Details regarding specific laboratory procedures/assessments to be performed in this trial are provided below. Laboratory tests for hematology, chemistry, urinalysis, and others are specified in Table 13.

Table 13. Laboratory Tests

Hematology	Chemistry	Urinalysis	Other
Hematocrit	Albumin		Serum β -human chorionic gonadotropin†
Hemoglobin	Alkaline phosphatase		(β -hCG)†
Platelet count	Alanine aminotransferase (ALT)		PT (INR)
WBC (total and differential)	Aspartate aminotransferase (AST)		aPTT
Red Blood Cell Count	Lactate dehydrogenase (LDH)		Total triiodothyronine (T3)
Absolute Neutrophil Count	Carbon Dioxide ‡		Free tyroxine (T4)
Absolute Lymphocyte Count	(CO_2 or bicarbonate)	Urine pregnancy test †	Thyroid stimulating hormone (TSH)
	Uric Acid		
	Calcium		
	Chloride		Blood for correlative studies
	Glucose		
	Phosphorus		
	Potassium		
	Sodium		
	Magnesium		
	Total Bilirubin		
	Direct Bilirubin (If total bilirubin is elevated above the upper limit of normal)		
	Total protein		
	Blood Urea Nitrogen		

† Perform on women of childbearing potential only. If urine pregnancy results cannot be confirmed as negative, a serum pregnancy test will be required.

‡ If considered standard of care in your region.

Laboratory tests for screening or entry into the Second Course Phase should be performed within 10 days prior to the first dose of treatment. After Cycle 1, pre-dose laboratory procedures can be conducted up to 4 days prior to dosing. Results must be reviewed by the investigator or qualified designee and found to be acceptable prior to each dose of trial treatment.

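### Table 2 sets the albumin minimum in mg/dL; read as written, the limit excludes nobody, and its unit and value need confirming

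*Combined protocol and SAP*

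**What the plan says.** Section 5.1.2, inclusion criterion 7, requires: "Demonstrate adequate organ function as defined in Table 2, all screening labs should be performed within 10 days of treatment initiation". Table 2 follows directly. Its hepatic block has rows for total bilirubin, AST and ALT, and albumin. The albumin row gives a minimum of 2.5 mg/dL.

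The hemoglobin row of the same table uses grams per deciliter with a molar equivalent: "9 g/dL or ≥ 5.6 mmol/L without transfusion or EPO dependency".

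Albumin appears once more as a laboratory test, in Section 7.2.3: "Laboratory tests for hematology, chemistry, urinalysis, and others are specified in Table 13". Table 13 lists albumin under chemistry, without a unit or a limit. No other part of the document states an albumin threshold or corrects the unit in Table 2.

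**The concern.** Serum albumin is normally reported in grams per deciliter or grams per liter. A minimum in single milligrams per deciliter is so low that it looks like a misprint in the unit.

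Two things are at stake, and both concern eligibility. First, the authors placed albumin beside bilirubin and the transaminases as a test of hepatic function at entry, and as printed that row does no screening. Second, the written rule and the probable intent give different answers for the same patient. Take a patient with an albumin of 2.0 g/dL, a value chosen only for illustration. Read literally, the patient passes the row. Read silently as g/dL, the patient fails it, although the text admits the patient. Section 12.1 places adherence to the eligibility requirements under institutional oversight, and Section 11.5 requires deviations to be reported. A monitor working from the printed text would find no deviation at any albumin value, while a monitor working from the presumed intent would apply an unwritten limit.

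**Working it through.** The plan derives no figure here, so there is nothing to reproduce. The check is a unit conversion and a comparison.

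**Inputs**

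- Printed minimum: 2.5 mg/dL (Table 2, albumin row).
- Conversion: 1 g/dL = 1,000 mg/dL.
- Serum albumin in patients: the documents give no range. Assumed range 1.0 to 5.0 g/dL, from very low to normal.

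**Step 1. Convert the printed limit.**

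2.5 mg/dL ÷ 1,000 = 0.0025 g/dL (0.025 g/L).

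**Step 2. Compare with the assumed range.** Ratio = (albumin in g/dL × 1,000) ÷ 2.5.

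| Assumed albumin (g/dL) | In mg/dL | Multiple of printed limit |
|---|---|---|
| 1.0 | 1,000 | 400 |
| 2.0 | 2,000 | 800 |
| 2.5 | 2,500 | 1,000 |
| 3.5 | 3,500 | 1,400 |
| 5.0 | 5,000 | 2,000 |

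Every value passes. Where in the range a patient falls makes no difference, because even the lowest assumed value exceeds the limit 400-fold.

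**Step 3. Size of the discrepancy if only the unit is wrong.**

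2.5 g/dL = 2,500 mg/dL, and 2,500 ÷ 2.5 = 1,000. This assumes that 2.5 is the number the authors meant. The documents do not settle that.

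**Step 4. Check the hemoglobin row, which carries two units.**

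Taking 16.114 g/mmol for the hemoglobin monomer (an assumption, not in the documents), 9 g/dL = 90 g/L, and 90 ÷ 16.114 = 5.59 mmol/L. The table prints 5.6. That row is internally consistent, so the check points to no general fault in the table's units.

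**Step 5. Could it be a fault of text extraction?** Unlikely. The row is intact and mg/dL is a complete, ordinary unit.

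**The case against.** The strongest reply is that this is a misprint with little practical effect.

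- **Other gates remain.** A patient with very low albumin must still meet the performance status and life expectancy criteria, the bilirubin, transaminase and coagulation limits in Table 2, and the blood pressure criterion. Exclusion 1 covers uncontrolled concomitant disease. Exclusion 16 lets the investigator keep out a patient over a laboratory abnormality. Section 7.2.3 requires the investigator or a designee to find laboratory results acceptable before each dose. This stands, and it limits the consequence. None of these provisions sets an albumin limit, so they are partial backstops and do not replace the row.
- **The intent is obvious, so nobody will read it literally.** Section 5.2.1 describes recruitment at one center, and Section 1.0 caps enrollment at 25. Nothing in the documents shows that anyone has applied the row literally. This also stands, although Sections 7.3.5.2 and 11.5 mention participating sites. It still leaves staff applying a rule that is not in the protocol.
- **Nothing statistical changes.** Correct. The sample size, error rates and endpoint definitions in Sections 7.1 and 9 do not use the albumin limit.

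A reader might infer a safety problem: that the faulty row exposes patients with low albumin to the hypotension and hepatic dysfunction known for IL-2. The documents do not support that reading. Section 4.6 reports those toxicities for high-dose systemic IL-2. For the intralesional route used here, Section 4.8.4 reports grade 3 toxicity in 2 of 187 patients (2 ÷ 187 = 1.1%), and Section 5.4.1.2 describes hypotension as rare, with one patient affected. The protocol nowhere links albumin to the toxicity of this regimen.

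**Conclusion.** The albumin limit in Table 2 is wrong as written. At any serum albumin from 1 to 5 g/dL the patient has 400 to 2,000 times the printed minimum, so the row excludes nobody. That range is an assumption, but the conclusion is not sensitive to it. The factor of 1,000 rests on a further assumption, that the number 2.5 is right and only the unit is wrong.

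The point is minor. It deserves correction because it sits in a binding entry criterion, but its reach is eligibility alone. Two stronger inferences should be resisted. One is that severely hypoalbuminemic patients are therefore eligible: passing one row does not make a patient eligible while the other criteria and exclusion 16 apply. The other is that the enrolled population has in fact varied with the reader: the documents show the ambiguity but no instance of divergent use.

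**What to change.** The investigators should confirm both the intended albumin limit and its unit, and correct the albumin row of Table 2. Any eligibility form derived from Table 2 should be checked against the corrected row; the documents do not include such a form, so this applies only if one exists. Since the row decides entry, the number should be confirmed at its source and not inferred from the unit used for hemoglobin.

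The cost is an edit to one table row, carried by a protocol amendment. The only downside is that a patient below the corrected limit, if there is one, would become ineligible; the documents give no basis for estimating how many. No analysis, sample size or endpoint text needs to change.
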